### 3.6.3.5 Additional Safety Endpoints

The following safety endpoints will be summarized descriptively for the safety analysis set by assigned infusion duration:

- The proportion of subjects who experienced IR leading to slowing down of the infusion rate or discontinuation of treatment (composite endpoint and for each individual component; separate analyses for reported events and adjudicated events) (safety analysis set).
- The proportion of subjects who completed all infusions over the assigned treatment duration length or a lesser time, without clinically requiring an increased infusion time (safety analysis set) will be summarized. Subjects who discontinue treatment prematurely will not be considered to have completed all infusions.
- The proportion of infusions completed over the assigned duration length or a lesser time, without clinically requiring an increased infusion time will be summarized for the safety analysis set on the infusion level and on the subject-specific level using two different denominators each:
  - Infusion level (will be reported as a proportion and a percentage):
    - The number of infusions completed over the assigned treatment duration length or a lesser time, without clinically requiring an increased infusion time / total number of infusions planned for all subjects (12 x number of subjects in the assigned treatment duration group).
    - The number of infusions completed over the assigned treatment duration length or a lesser time, without clinically requiring an increased infusion time / total number of infusions completed prior to discontinuation of treatment planned for all subjects.
  - Within-subject level (reported descriptively as a continuous variable with 95% sign test-based confidence intervals provided around the median):
    - For each subject, the subject-specific number of infusions completed over the assigned treatment duration length or a lesser time, without clinically requiring an increased infusion time / subject's total number of infusions planned (12 total).
    - For each subject, the subject-specific number of infusions completed over the assigned treatment duration length or a lesser time, without clinically requiring an increased infusion time / subject's total number of completed infusions prior to discontinuation of treatment.
- The time to subjects' first IR and first instance of IR leading to discontinuation of treatment or slowing down of the infusion rate will be analyzed. KM estimates of the time to event from Day 1 will be reported along with the corresponding quartiles and a 95% CI for the median time (if available). The event "first instance of IR leading to discontinuation of treatment or slowing down of the infusion rate" will be analyzed both as a composite endpoint and individually.

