###### **Pegloticase**

All subjects will receive pegloticase at a dose of 8 mg administered IV every 2 weeks for a total of 12 infusions from Day 1 through Week 24, inclusive (Pegloticase + MTX Period). Subjects will not be fasting on the day of infusion and will be encouraged to have a snack or normal meal

before or after the infusion. Pre-infusion SUA results must be reported by the local or central laboratory prior to pegloticase infusion (see Section 9.6.2.1).

Standardized IR prophylaxis consisting of pre-treatment with antihistamines, acetaminophen and corticosteroids will accompany each infusion (see Section 9.5.2.3).

Pegloticase will be administered either as a ready-to-use 0.16 mg/mL IV solution (50 mL) or an admixture of 8 mg in 50 mL of 0.45% or 0.9% Sodium Chloride Injection, USP for IV infusion by gravity feed or infusion pump. After approximately 30 subjects in 30 min cohort receive admixture of 8 mg in 50 mL of 0.45% or 0.9% Sodium Chloride Injection, USP for IV infusion, newly enrolled subjects will be assigned to ready-to-use 0.16mg/mL IV solution (50 mL). Pegloticase will not be administered as an IV push or bolus.

In a patient with IV site, using tubing with no in-line filter, the pegloticase preparation will be infused over approximately 30 to 60  $\pm$ 5 minutes, depending on cohort assignment, while the subject is under close observation for any signs of distress. If an in-line filter is used, it should be 0.2  $\mu$ m or larger. At the end of the infusion, the IV line will be flushed with 10 mL of normal saline to ensure the full dose is administered. The date and time of infusion start and stop (inclusive of the IV flush) will be recorded.

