### **9.5.11 Treatment Compliance**

A dosing calendar will be provided to subjects at the Week -4 Visit for recording each dose of MTX on each calendar day of MTX administration (Additional calendar pages may be provided at future visits as required). The dosing calendar and bottle of MTX should be brought to each study visit for assessment of compliance with MTX. Adherence to the MTX regimen will also be recorded by the study coordinator at study visits in the eCRF by recording the date of each MTX dose (mg), frequency and time of each dose per calendar day. Subjects who have taken at least 80% of the protocol specified amount of MTX will be considered compliant. Noncompliant subjects will be re-educated on compliance.

At study visits, the subject will be asked a Yes/No question whether folic acid, gout flare and IR prophylaxis were administered.

Pegloticase will be administered at the study site by trained personnel. The date and time of infusion start and stop (inclusive of the 10-mL flush) will be recorded.

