### 3.6.2 Extent of Exposure

Study drug exposure will be summarized by ‘as assigned’ infusion duration group for the following statistics: duration of treatment (in days), number of infusions (pegloticase only), and total dose received for MTX and pegloticase.

The usage of prophylaxis treatments (folic acid, IR usage of fexofenadine the day prior to pegloticase infusion, IR prophylaxis of fexofenadine and acetaminophen the morning prior to infusion, and IR prophylaxis of methylprednisolone immediately prior to infusion) will be provided in listings only. Reasons for infusion interruptions will be provided in the listings.

For the MTX Run-in Period, the following will be summarized using the ITT analysis set:

- Days in MTX Run-in Period
- Duration of treatment, defined as the Day 1 visit date – first dose date of MTX for subjects in the mITT analysis set and last dose of MTX – first dose of MTX + 1 for subjects who do not continue into the Pegloticase + MTX Treatment Period (summarized with descriptive statistics of mean, SD, median, minimum, and maximum)
- Total MTX dose taken between the first and last dose dates in the MTX Run-in Period, inclusive (in mg) (summarized with descriptive statistics of mean, SD, median, minimum, and maximum)
- Average weekly MTX dose (in mg) (total dosage for the MTX Run-in Period divided by number of doses taken during the MTX Run-in Period divided by [days in MTX Run-in Period / 7]) (summarized with descriptive statistics of mean, SD, median, minimum, and maximum)
- Number of subjects with MTX dosage reductions from planned 15 mg/week.

For the Pegloticase + MTX Period, the following will be summarized for the safety analysis set:

- Pegloticase
  - Days in Pegloticase + MTX Period
  - Duration of Pegloticase exposure in days defined as the last Pegloticase date – first Pegloticase dosing date + 1 (summarized with descriptive statistics of mean, SD, median, minimum and maximum)
  - Number of pegloticase infusions received (summarized with frequency summary and also with descriptive statistics of mean, SD, median, minimum, and maximum)
  - Duration of Pegloticase infusion in minutes
  - At least one planned infusion duration changed from assigned infusion duration
  - Proportion of subjects planned duration different from assigned infusion duration

- At each scheduled Pegloticase infusion visit the following will be summarized:
  - Number of subjects receiving a complete infusion (i.e. full dose administered)

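### Does the saline flush leave the SAP's on-time infusion endpoint undefined?

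*SAP*

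**What the plan says.** SAP 3.6.3.5 words the endpoint thus: "The proportion of subjects who completed all infusions over the assigned treatment duration length or a lesser time, without clinically requiring an increased infusion time". Alongside it, that section gives an infusion-level version with two denominators (planned and completed infusions) and two within-subject ratios. It states no stop-time convention and no tolerance.

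Protocol 9.5.7.3.1.2 describes administration. The product is given "either as a ready-to-use 0.16 mg/mL IV solution (50 mL) or an admixture of 8 mg in 50 mL", with saline as diluent in the second case. The preparation runs for about 30 to 60 minutes, with a tolerance of plus or minus "5 minutes, depending on cohort assignment". Next comes the flush: "At the end of the infusion, the IV line will be flushed with 10 mL of normal saline". A recording rule then fixes which clock times go into the record: "The date and time of infusion start and stop (inclusive of the IV flush) will be recorded". Protocol 9.5.11 gives this rule again in nearly the same form: "The date and time of infusion start and stop (inclusive of the 10-mL flush) will be recorded".

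SAP 3.6.2 lists "Duration of Pegloticase infusion in minutes" with no derivation. As separate items it lists "At least one planned infusion duration changed from assigned infusion duration" as well as how many subjects had planned and assigned durations that differed. The SAP does not mention the flush.

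**The concern.** The assigned duration describes the drug preparation, while the recorded interval covers drug plus flush. The wording of the endpoint, completion within the assigned time or less, can be read as elapsed time. A programmer who subtracted recorded start from recorded stop and required the result not to exceed the assigned duration would fail infusions that were on time and well tolerated.

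The subject-level endpoint needs every infusion to qualify, so one reclassified infusion out of 12 changes a subject's result. Two stated safety objectives depend on these summaries, in a trial whose subject is infusion duration. The study is open-label, so a rule left unstated could be settled with data in view. The source for a clinical need for more time is not named in SAP 3.6.3.5 either.

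**Working it through.** The plan states no figure for this endpoint, so there is none to reproduce. The check has two parts: what a literal recorded-time rule would do, and which rule the rest of the plan supports.

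**1. Literal recorded time**

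Inputs from Protocol 9.5.7.3.1.2: volume 50 mL; assigned time D = 30, 45 or 60 min; flush 10 mL; tolerance 5 min, read here as applying around each assigned duration. The flush rate is not given and is assumed.

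- Drug rate = 50 / D.
- Flush time at that rate = 10 / (50 / D) = D / 5.
- Recorded time = D + D / 5.

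| D (min) | Drug rate (mL/min) | Flush at drug rate (min) | Recorded (min) | D + 5 (min) | Recorded with 1-min flush (min) |
|---|---|---|---|---|---|
| 30 | 1.67 | 6 | 36 | 35 | 31 |
| 45 | 1.11 | 9 | 54 | 50 | 46 |
| 60 | 0.83 | 12 | 72 | 65 | 61 |

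With 51 mL (1 mL of drug added to a 50 mL bag) the recorded times are 35.88, 53.82 and 71.76 min, which gives the same classification.

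With no tolerance, any flush longer than zero fails an infusion whose drug ended exactly on time. With +5 min, the outcome depends on the flush rate. The flush must take no more than 5 min, so the rate must be at least 10 / 5 = 2 mL/min. That is 2 / 1.67 = 1.2, 2 / 1.11 = 1.8 and 2 / 0.83 = 2.4 times the drug rate. A 1-minute flush passes with +5 in every cohort; a flush at the drug rate fails in every cohort.

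The literal rule would therefore give a poor result. The documents do not show how often, because they give no flush rate.

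**2. Which duration the plan uses**

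- SAP 3.1.2 defines as-treated groups of 60, 45, 30 and more than 60 minutes. Recorded times of 36 or 54 min belong to none of them, and an on-time 60-minute infusion with any flush would move into the group above 60. The grouping works only on nominal durations.
- SAP 3.1.6 works its example with nominal 60- and 120-minute infusions.
- SAP 3.3.1 tabulates shifts from the assigned duration to other durations.
- SAP 3.6.2 summarises planned against assigned duration directly.

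Under planned versus assigned, the example infusion passes in all three cohorts, because 30 ≤ 30, 45 ≤ 45 and 60 ≤ 60. The flush does not enter.

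**3. Whether the protocol contradicts itself on the stop time**

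It does not. The flush sentence describes a step in administration, with delivery of the full dose as its purpose. The recording sentence says which clock time goes in the record, and Protocol 9.5.11 agrees. One recorded stop is defined, and it includes the flush.

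**4. Data on clinically needed changes**

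Protocol 9.5.7.3.2.4 has changes of infusion rate or dilution recorded in the eCRF after an infusion reaction. Protocol 9.5.7.3.2.1 has total volume and duration captured when later infusions use a larger volume. Data relevant to the clinical condition in the endpoint are therefore collected, although SAP 3.6.3.5 does not name the field.

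**The case for a change.** The strongest argument for a change is that SAP 3.6.3.5 never uses the term planned duration. SAP 3.6.2 lists planned duration and infusion minutes as separate items, and the endpoint's wording suits elapsed time. Two competent programmers could produce different tables. The qualifier about clinical need can be read as an extra condition, in which case it does not excuse the flush. Planned duration also has a weakness: it does not show an infusion that was slowed partway through.

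Part of this stands. The SAP does not name the variable, and recorded minutes should not be set directly against the assigned duration.

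The rest carries less weight. A recorded-time rule without a flush adjustment would fail almost every infusion run exactly to plan, which an analyst would notice at once. Slowing caused by an infusion reaction has its own endpoint in SAP 3.6.3.5 and its own eCRF record. The open-label point applies equally to a clarification written now, since the SAP is dated January 2024. Labelling the minutes in a table as including the flush is a matter of table format, which SAP 3.1.1 leaves to a companion document and allows to change without an amendment.

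**Conclusion.** No change to the plan is needed. The SAP leaves a definition unwritten, but its use of nominal durations in SAP 3.1.2, 3.1.6, 3.3.1 and 3.6.2 points to planned versus assigned duration, read together with the eCRF record of clinically required changes. On that basis an on-time infusion is classified correctly in all three cohorts at any flush rate. The as-treated grouping in SAP 3.1.2 is nominal for the same reason and is not affected.

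The harm appears only under a literal comparison of recorded with assigned minutes. With the 5-minute allowance it further requires a flush slower than 2 mL/min, if the drug itself ends exactly on time. The effect on the reported proportions cannot be estimated from the documents, and no bias between cohorts is shown. The summaries are descriptive: Protocol 9.7.5 and SAP 3.1.1 rule out statistical testing. The primary infusion-reaction analysis, the endpoint on slowing or discontinuation after an infusion reaction, and the sample size of 110 do not depend on these times.

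This conclusion assumes that planned duration is available per infusion, as SAP 3.6.2 implies, and that the eCRF identifies clinically driven changes. The eCRF itself was not available to confirm the second point.

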In the phase 3 pivotal studies, deaths, AEs, SAEs, as well as the laboratory abnormalities were generally equally distributed across placebo and pegloticase treatment groups, with the clear exception of gout flares and IRs. Pegloticase-treated subjects exhibited a higher rate of gout flares during Months 1-3 as uric acid was being acutely lowered, then a decrease in gout flares vs. placebo during Months 4-6. Despite use of prophylactic medications against hypersensitivity including administration of corticosteroids, antihistamine and acetaminophen in advance of each pegloticase infusion, IRs were seen in 22/85 (26%) of subjects receiving the 8 mg 2 week regimen. There was no specified definition of anaphylaxis in the Phase 3 protocols and there were no investigator-reported events of anaphylaxis in the Phase 3 studies with pegloticase. However, in a post-hoc review applying the NIAID/FAAN criteria (Sampson et al., 2006), it was determined that across the Phase 2 and Phase 3 program, anaphylaxis occurred in 6.5% of subjects treated with pegloticase dosed every 2 weeks. Anaphylaxis generally occurred within 2 hours after treatment. Manifestations included wheezing, peri-oral or lingual edema, or hemodynamic instability, with or without rash or urticaria. All of these events had relatively rapid resolution with the cessation of infusion.

In a post-hoc analysis, the apparent role of immunogenicity in both loss of urate lowering effect and incidence of IRs was appreciated. Only 2% of subjects with anti pegloticase antibody titers exceeding 1:2430 maintained a urate-lowering response to pegloticase compared with 63% of subjects who were treated for at least 2 months without developing high-titer antibodies ( $p < 0.001$ ) (Sundy et al., 2011). The incidence of IRs was higher among subjects who developed high-titer antibodies compared with those who had titers that did not exceed 1:2430 (60% vs 19%;  $p < 0.001$ ) (Sundy et al., 2011). In addition, most IRs occurred when sUA levels were greater than 6 mg/dL. Retrospective analyses showed that the loss of urate-lowering efficacy, as reflected by sUA of greater than 6 mg/dL, preceded a patient's first IR, whenever it occurred, in 20 (91%) of 22 subjects treated with pegloticase every 2 weeks.

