## 1.2 Efficacy Assessments

### 1.2.1 Serum Uric Acid

Serum samples for measurement of sUA levels will be collected at the Screening Visit, Week -4 and Week -2 Visits during the MTX Run-in Period; within 48 hours prior to each pegloticase infusion and after the end of each pegloticase infusion prior to discharge, from Day 1 in the Pegloticase + MTX Period through Week 22; and at the End of Pegloticase Infusion Visit (if applicable); at the Week 24/End of study/Early Termination Visit and Month 3 Post-Treatment Follow-Up visits.

A subject with pre-infusion sUA level > 6 mg/dL (based on the local or central laboratory) at 2 consecutive study visits, beginning with the Week 2 Visit, will be discontinued from pegloticase treatment and remain on study.

Samples that result in discordant results between local and central laboratories will be evaluated and discussed with the Investigator and the Sponsor's Medical Monitor on a case-by-case basis to determine whether the subject should continue on study or discontinue.

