### 3.4 Endpoint Analysis

Potential intercurrent events (ICE) like discontinuing from the treatment may occur during the study. Subjects who discontinue from the treatment will be encouraged to stay in the study after and data will be collected through planned study completion. These intercurrent events will be addressed using different strategies in the efficacy and safety analyses as appropriate.

In general, treatment policy strategy will be used to account for the ICEs for defining estimands corresponding to continuous efficacy endpoints. For binary responder endpoints, composite strategy will be used. Safety endpoints will be assessed using a while-on-treatment strategy.

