Time to event to each individual component of the composite endpoint will also be summarized descriptively. To account for the competing events nature of these events, the cumulative incidence function will be determined and estimates of the cumulative incidence by Week 24 and median time to event for each event will be summarized with a 95% CI for the median time (if available). Subjects who do not experience any of the competing events or the event of interest will be censored at the date of their last infusion.

A competing event is defined as any of the components of the composite endpoint or discontinuation from treatment for any reason. Other competing events may be included in the analysis, as needed.

The time to an event will be calculated by date of event – date of first dose of treatment + 1. Patients who do not experience an event will be censored at time given by date of last dose of treatment - date of the first dose of the treatment + 1.

Events of anaphylaxis and IRs are collected as “reported events” and “adjudicated events”. For all relevant endpoints, separate analyses will be created for reported events and adjudicated events.

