### 3.5.2 Anti-Drug Antibodies

Immunogenicity of pegloticase will be assessed in serum samples by evaluating anti-PEG and anti-uricase IgG antibodies. Samples will be collected prior to the pegloticase infusion on Day 1 and at the Weeks 2, 6, 12, 20 and the End-of-study (Week 24)/Early Termination Visit and 3-month Post-Treatment Follow-up Visits. In the event of an AE suspected to be an IR, a serum sample will be collected at that time or at the subsequent visit for evaluation of pegloticase/PEG antibodies.

For anti-PEG IgG antibodies, using the safety analysis set, the number and percentage of subjects who meet the following criteria will be summarized by scheduled timepoint and overall:

- ADA positive at pegloticase baseline
- ADA negative at pegloticase baseline
- ADA negative at pegloticase baseline and ADA positive at post-pegloticase baseline
  - ADA positive at pegloticase baseline with increase in titer from pegloticase baseline
  - ADA negative at pegloticase baseline and ADA positive at post-pegloticase baseline or with increase in titer from pegloticase baseline (i.e. ADA positive status post-baseline)

For anti-uricase IgG antibodies, the number and percentage of subjects with ADA positive at pegloticase baseline and post-pegloticase baseline will be summarized by scheduled timepoint.

Kaplan-Meier estimates of the time to positive anti-PEG response (for subjects who were negative at baseline) or increase in anti-PEG titer (for subjects who were positive at baseline), and the time to anti-uricase response with 25th percentile, median, 75th percentile, and 95% CI, along with a Kaplan-Meier curve will be produced. Subjects who never have a positive anti-PEG response or increase in titer will be censored at the date of their last visit (3 month follow up visit, or, if the subject did not attend this visit, then whatever last visit they have on record). Antibody result from both scheduled and unscheduled visits will be included for the time to event analysis.

Anti-PEG and anti-uricase titer will be summarized descriptively with mean and CV% by study visit. Additionally, Anti-PEG titers at the last pegloticase infusion and post-treatment will be summarized for ADA positive post-baseline subjects.

All results will be presented by ‘as assigned’ infusion duration group.

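### Time to first infusion reaction is planned as Kaplan-Meier with no censoring rule and no competing event, although the SAP uses cumulative incidence elsewhere for one of the same events

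*SAP*

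**What the plan says.** SAP 3.6.3.5 covers time to first IR and time to first IR leading to discontinuation or slowing of the infusion. For both, "KM estimates of the time to event from Day 1 will be reported", with quartiles and, if available, a confidence interval for the median. The second event is analysed as a composite and by its parts, so IR leading to discontinuation is itself a Kaplan-Meier endpoint here. The section does not say when a subject without an event is censored, or how stopping pegloticase is handled.

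SAP 3.4.2.2 treats IR leading to discontinuation as a component of the secondary composite. There the SAP says: "To account for the competing events nature of these events, the cumulative incidence function will be determined". It adds: "A competing event is defined as any of the components of the composite endpoint or discontinuation from treatment for any reason". Its censoring rule is: "Patients who do not experience an event will be censored at time given by date of last dose of treatment".

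Three other provisions bear on the point:

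- SAP 3.4: "Safety endpoints will be assessed using a while-on-treatment strategy".
- SAP 1.2.1: a subject who meets the serum uric acid (sUA) stopping rule "will be discontinued from pegloticase treatment and remain on study". Last dose and last visit can therefore be far apart.
- SAP 3.5.2: in the antibody Kaplan-Meier analysis, subjects without an event "will be censored at the date of their last visit".

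Protocol 9.7.7, and the statistical part of the protocol synopsis, also plan Kaplan-Meier for these IR endpoints.

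**The concern.** A subject who stops pegloticase without an IR can no longer have an on-treatment IR. For a while-on-treatment question, stopping is a competing event, and SAP 3.4.2.2 applies that reasoning to the components of the composite. SAP 3.6.3.5 does not, and gives no reason for the difference.

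Two things follow. IR leading to discontinuation would be estimated by two methods in the same cohort, and the two curves need not agree. In addition, because 3.6.3.5 has no censoring rule, two programmers could produce different curves for time to first IR and both be within the SAP. Under one natural choice, censoring at last dose, Kaplan-Meier treats stopped subjects as if they had continued at the same risk as those still infused. It then shows more risk than was observed on treatment.

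**Working it through.** **The plan's own figure.** SAP 1.1.3 expects a 5.0% IR rate with n = 110 and claims a probability above 80% that the two-sided 95% exact upper bound is below 13%. The Clopper-Pearson upper bound is 12.67% for 7/110 and 13.83% for 8/110, so at most 7 subjects with an IR are allowed. P(X ≤ 7 | 110, 0.05) = 81.4%, so the claim reproduces. It uses the crude proportion, and nothing below changes it.

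**Inputs.** On-treatment IR risk c = 5% (SAP 1.1.3). Twelve infusions (SAP 1.1.2). The fraction d stopping without an IR is not in the documents, so I assume 10% to 40%.

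**Case A: stopped subjects censored at last dose.** Let h be the IR probability per infusion among those still treated, and s the probability of stopping after an infusion in the stopping window. With a(k) the share still at risk at infusion k:

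- cumulative incidence = Σ a(k)·h
- fraction stopping = Σ a(k)·(1 − h)·s over the window
- one minus Kaplan-Meier = 1 − (1 − h)^12

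I solved h and s so that cumulative incidence is exactly 5% and the stopping fraction is exactly d. Even stopping means after infusions 2 to 11; early stopping means after infusions 3 to 6. Under the sUA rule the earliest stop is after infusion 2, because two visits from Week 2 on are needed. For example, with d = 20% and even stopping, h = 0.004733, s = 0.02281, and 1 − (1 − 0.004733)^12 = 5.53%.

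| Stopping fraction d | Even: 1−KM | Excess (points) | Early: 1−KM | Excess (points) |
|---|---|---|---|---|
| 10% | 5.25% | 0.25 | 5.34% | 0.34 |
| 20% | 5.53% | 0.53 | 5.73% | 0.73 |
| 30% | 5.87% | 0.87 | 6.19% | 1.19 |
| 40% | 6.26% | 1.26 | 6.75% | 1.75 |

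A closed form under proportional cause-specific hazards gives a cross-check: 1−KM = 1 − exp{[c/(c+d)]·ln(1−c−d)}. For d = 10%, c/(c+d) = 1/3 and ln(0.85) = −0.1625, giving 5.3%. For d = 20%, 30% and 40% it gives 5.6%, 6.0% and 6.4%.

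Timing also matters. With c = 5% and d = 30%, fixed timing patterns give 5.2% when IRs fall in the first four infusions and stops are even, and 7.1% when stops are early and IRs fall in the last six infusions.

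**Case B: stopped subjects kept at risk to Week 24.** No one leaves the risk set before the last infusion, so one minus Kaplan-Meier equals the crude proportion, 5.0%. There is no excess. Subjects who also leave the study would bring some of it back.

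**Cumulative incidence with stopping as the competing event.** This returns c = 5% in every row, which is the on-treatment risk.

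**Planned summaries.** The lower quartile needs the curve to reach 25%. Even at an IR risk of 13% with 50% stopping, the closed form gives 18.6%. At the expected rate, neither the quartiles nor the median would be reached, so the curve is the only informative output.

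**The case against.** The strongest objection is that 3.6.3.5 never says stopped subjects are censored at last dose. That rule belongs to 3.4.2.2. The antibody analysis uses last visit, and subjects who stop under the sUA rule remain on study. This stands: the overstatement is conditional. Last-dose censoring is the more natural reading, because it is the SAP's only rule for time to IR events and it fits the while-on-treatment strategy, but it is inferred.

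The inconsistency is also narrower than it first looks. SAP 3.4.2.2 uses cumulative incidence only for the components; the composite itself is analysed by Kaplan-Meier with censoring at last infusion. Time to first IR is not one of those components. The direct clash is for IR leading to discontinuation. For time to first IR the argument is that the same reasoning applies.

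A reader might go further and infer any of three things that the documents do not support:

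- **Conflicting Week 24 IR risks will be reported.** SAP 3.6.3.5 plans no Week 24 figure, so only a plotted or tabulated curve can differ.
- **Informative censoring makes the overstatement worse.** Protocol 7.1.2 reports that loss of urate lowering preceded the first IR "whenever it occurred, in 20 (91%) of 22 subjects treated with pegloticase every 2 weeks". That is the share of first IRs preceded by high sUA, not the IR risk among those stopped. If stopped subjects were at higher risk, Kaplan-Meier would understate the risk had they continued, which is a different quantity and the opposite direction. The excess over on-treatment risk arises whether or not stopping is informative.
- **The primary result is at risk.** SAP 3.4.1 uses the crude proportion with an exact interval.

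Finally, the on-treatment picture is available elsewhere: the primary proportion, and the count of first events by infusion number in SAP 3.6.3.4. That limits the harm but does not settle which curve should be drawn.

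**Conclusion.** The point holds as a minor inconsistency and a gap in specification. SAP 3.6.3.5 leaves out the censoring rule and the competing event, and it uses a different method from 3.4.2.2 for IR leading to discontinuation.

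If last-dose censoring is applied, the curve overstates the on-treatment IR risk. At a true 5%, the excess is about 0.3 to 1.3 points when 10-40% stop evenly and about 0.7 to 1.8 points when 20-40% stop early. In a cohort of 110, one point is about one subject (0.01 × 110 = 1.1). If stopped subjects remain at risk to their last visit, the excess largely disappears.

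These sizes rest on assumed stopping fractions and, in the table, on a constant IR hazard per infusion. The direction under last-dose censoring needs neither assumption, only that some subjects stop before later IRs occur. No decision in the plan depends on the curve.

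**What to change.** In SAP 3.6.3.5:

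1. State the censoring rule for subjects without the event, including those who complete all infusions.
2. Replace Kaplan-Meier with the cumulative incidence function of 3.4.2.2 for time to first IR and for time to first IR leading to discontinuation or slowing, as a composite and individually. The competing event is pegloticase discontinuation without the IR event of interest.
3. Report cumulative incidence at Week 24 with a 95% CI, since the median and quartiles will not be reached at the expected rate.
4. Record this in SAP Section 4 as a change from the Kaplan-Meier analysis in protocol 9.7.7. SAP 3.1 already lets the SAP supersede the protocol's statistical sections.

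Kaplan-Meier may be kept as a supplementary display with its censoring rule stated. The cost is SAP wording and documentation of the change. The method is already planned for 3.4.2.2, and neither data collection nor sample size changes.
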